6.13.2.2. Severe Persistent Hyperglycemia

A summary of initiation of rescue therapy in response to severe, persistent hyperglycemia will be provided by treatment. If there are a sufficient number of episodes, time-to-first event analyses for the initiation of rescue therapy will be conducted by treatment using a cox proportional regression model. A listing of patients who initiated rescue therapy will be provided.

6.13.2.3. Pancreatitis

Summaries of adjudicated and investigator-reported pancreatic events will be provided by treatment. Determination of investigator-reported events will be through the predefined Standardized MedDRA Queries (SMQ) search for acute pancreatitis and MedDRA PT of pancreatitis chronic. Detailed searching criteria can be found in [Appendix 1](#). Treatment-emergent adjudication-confirmed pancreatitis will be considered an AESI.

6.13.2.3.1. Pancreatic Enzyme Assessment

Observed pancreatic enzyme data (p-amylase and lipase) will be summarized by treatment and nominal visit. The number and proportion of patients with pancreatic enzyme values exceeding the following thresholds will be provided by treatment, baseline pancreatic enzyme value (\leq Upper Limit of Normal [ULN], $>$ ULN), and nominal visit: (>1 to ≤ 3) \times ULN, (>3 to ≤ 5) \times ULN, (>5 to ≤ 10) \times ULN, $>10 \times$ ULN.

Additionally, the number and proportion of patients with maximum postbaseline pancreatic enzyme values exceeding the following thresholds will be provided by baseline pancreatic enzyme value (\leq ULN, $>$ ULN) and treatment: (>1 to ≤ 3) \times ULN, (>3 to ≤ 5) \times ULN, (>5 to ≤ 10) \times ULN, $>10 \times$ ULN.

An MMRM analysis will be used to analyze each pancreatic enzyme with a log transformed (postbaseline measure/baseline measure) response variable and stratification factors, treatment, nominal visit, and treatment-by-nominal visit interaction as fixed effects, baseline value as a covariate

6.13.2.4. Thyroid Safety Monitoring

Treatment-emergent thyroid malignancies and C-cell hyperplasia will be identified using predefined MedDRA high level terms (HLTs) of thyroid neoplasms malignant and PT of thyroid C-cell hyperplasia. Detailed searching criteria can be found in [Appendix 1](#). A summary by treatment and PT, PT within SMQ, and HLT will be provided. Thyroid malignancies and C-cell hyperplasia will be considered AESIs.

6.13.2.4.1. Calcitonin

Observed calcitonin data will be summarized by treatment and nominal visit. Additionally, the number and proportion of patients with a calcitonin value exceeding the following thresholds will be provided by treatment, baseline calcitonin value (≤ 20 ng/L, >20 ng/L), nominal postbaseline visit, and postbaseline calcitonin categories: ≤ 20 ng/L, >20 ng/L to ≤ 35 ng/L, >35 ng/L to ≤ 50 ng/L, >50 ng/L to ≤ 100 ng/L, >100 ng/L.

Additionally, the number and proportion of patients with a maximum postbaseline calcitonin value exceeding the following thresholds will be provided by treatment and baseline calcitonin value (≤ 20 ng/L, >20 ng/L): ≤ 20 ng/L, >20 ng/L to ≤ 50 ng/L, >50 ng/L to ≤ 100 ng/L, >100 ng/L.

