- [21] Have family or personal history of medullary thyroid carcinoma (MTC) or multiple endocrine neoplasia syndrome type 2 (MEN-2)

- [22] Have a serum calcitonin level of ≥ 35 ng/L (pg/mL), as determined by central laboratory at Visit 1
- [23] Known or suspected hypersensitivity to trial product(s) or related products
- [24] Have evidence of a significant, active autoimmune abnormality (for example, lupus or rheumatoid arthritis) that, in the opinion of the investigator, is likely to require concurrent treatment with systemic glucocorticoids in the next 12 months
- [25] Have had a transplanted organ (corneal transplants [keratoplasty] allowed) or awaiting an organ transplant
- [26] Have a history of an active or untreated malignancy, or are in remission from a clinically significant malignancy (other than basal or squamous cell skin cancer, in situ carcinomas of the cervix, or in situ prostate cancer) for less than 5 years
- [27] Have a history of any other condition (such as known drug or alcohol abuse or psychiatric disorder) that, in the opinion of the investigator, may preclude the patient from following and completing the protocol
- [28] Have any hematological condition that may interfere with HbA1c measurement (for example, hemolytic anemias, sickle-cell disease)

Prior/Concomitant Therapy

- [29] Treatment with any glucose lowering agent(s) other than stated in the inclusion criteria # 2 in a period of 2 months prior to Visit 1 and between Visit 1 and Visit 3
- [30] Have been treated with prescription drugs that promote weight loss (e.g., Saxenda (liraglutide 3.0 mg), Xenical® [orlistat], Meridia® [sibutramine], Acutrim® [phenylpropanolamine], Sanorex® [mazindol], Apidex® [phentermine], BELVIQ® [lorcaserin], Qsymia™ [phentermine/topiramate combination], contrave® [naltrexone/bupropion] or similar other body weight loss medications including over-the-counter [OTC] medications [e.g., alli®]) within 3 months prior to Visit 1 and/or between study entry (Visit 1) and randomization (Visit 3)
- [31] Are receiving chronic (>2 weeks or 14 days) systemic glucocorticoid therapy (excluding topical, intra-ocular, intranasal, or inhaled preparations) or have received such therapy within 1 month of Visit 1; or between Visits 1 and 3

Prior/Concurrent Clinical Trial Experience

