9.2.2.4. Thyroid Malignancies and C-Cell Hyperplasia

Individuals with personal or family history of MTC and/or MEN-2 will be excluded from the study. The assessment of thyroid safety during the trial will include reporting of any case of thyroid malignancy including MTC and papillary carcinoma and measurements of calcitonin. This data will be captured in specific eCRFs. The purpose of calcitonin measurements is to assess the potential of tirzepatide to affect thyroid C-cell function, which may indicate development of C-cell hyperplasia and neoplasms. Tirzepatide should be discontinued (after first confirming the value) if post randomization calcitonin value is ≥ 35 ng/L (pg/mL) and has increased at least 50% over baseline. A consultation with a thyroid specialist (if not available, an endocrinologist) should be obtained.

If the increased calcitonin value (≥ 35 pg/mL and increases by $\geq 50\%$ compared to baseline) is observed in a patient who has administered a medication that is known to increase serum calcitonin, this medication should be stopped and calcitonin levels should be measured after an appropriate wash out period. If the confirmed calcitonin value is < 35 pg/mL, tirzepatide should be restarted when it is safe to do so.

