4.4. Safety Objectives

To compare the safety of tirzepatide 5 mg, 10 mg, and 15 mg to insulin glargine for:

- treatment-emergent adverse events (TEAEs)
- early discontinuation of study drug due to adverse events (AEs)
- adjudicated pancreatic AEs
- serum calcitonin
- incidence of allergic and hypersensitivity reactions
- incidence of treatment-emergent anti-drug antibodies to tirzepatide
- mean change in systolic and diastolic blood pressure and heart rate from baseline
- occurrence of hypoglycemic episodes
- incidence of initiation of rescue therapy for severe, persistent hyperglycemia

[figure not shown]
5. Study Design

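### The SAP's maximum-postbaseline calcitonin table drops the 35 ng/L cut, so the calcitonin tables bound but do not give the number of patients per arm reaching the protocol's threshold

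*SAP*

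**What the plan says.** SAP 4.4 lists "serum calcitonin" among the safety measures on which each tirzepatide dose is compared with glargine. SAP 6.13.2.4.1 plans three outputs for it:

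- Descriptive summaries by treatment and visit.
- A category table by treatment, baseline (≤20 or >20 ng/L), "nominal postbaseline visit, and postbaseline calcitonin categories". Its classes are ≤20, >20 to ≤35, >35 to ≤50, >50 to ≤100 and >100 ng/L.
- A category table of each patient's highest postbaseline value, which "will be provided by treatment and baseline calcitonin value" (same two strata). Its classes are ≤20 ng/L, then ">20 ng/L to ≤ 50 ng/L, >50 ng/L to ≤ 100 ng/L, >100 ng/L".

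Protocol 9.2.2.4 sets the action criterion at a postrandomization value of 35 or more "ng/L (pg/mL) and has increased at least 50% over baseline", to be applied "after first confirming the value". Protocol 8.1.1 states the same rule but gives the 35 in ng/mL. Exclusion [22] removes patients who "Have a serum calcitonin level of" 35 ng/L or more at Visit 1. The Schedule of Activities places postbaseline calcitonin at Weeks 12, 24 and 40, early termination and Visit 801.

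**The concern.** The maximum table is the one calcitonin-specific table that counts each patient once over the whole study, and it has lost the cut that matches the protocol's threshold. Patients who reach 35 ng/L and patients who stay well below it share the >20 to ≤50 cell. The by-visit table keeps a cut at 35, but it counts patients per visit, and its boundary differs from the protocol's at exactly 35. No calcitonin table uses the percentage rise. The neighbouring pancreatic enzyme section (SAP 6.13.2.3.1) uses the same classes in its by-visit and maximum tables, so calcitonin is the exception.

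At stake is a plain safety comparison: how many patients in each arm reached the protocol's own calcitonin threshold at any time.

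**Working it through.** The plan states no figure to reproduce, so the check asks which table cells determine whether a patient meets the criterion. It reads the threshold in ng/L, as in protocol 9.2.2.4, exclusion [22] and the SAP tables. Baselines are taken as below 35 ng/L, as exclusion [22] implies for correctly enrolled patients.

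**1. Criterion.** Met if value ≥ 35 and value ≥ 1.5 × baseline.

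**2. Where the 50% rule matters.**
- Baseline 20: 35/20 − 1 = 0.75. For any baseline ≤20, a value ≥35 is a rise of at least 75%, so the percentage rule is met automatically.
- The rule starts to bind at baseline 35/1.5 = 23.3 ng/L.
- Baselines stay below 35 and 1.5 × 35 = 52.5, so it can decide status only for values from 35 up to 52.5 ng/L.

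**3. Cells of the maximum table.** Baseline and postbaseline values were enumerated in steps of 0.1 ng/L.
- Baseline ≤20: only >20 to ≤50 is mixed. With baseline 10, maxima of 25 (not met) and 40 (met) share it.
- Baseline >20: >20 to ≤50 is mixed. So is >50 to ≤100: baseline 34.9 with maximum 51 is a rise of 51/34.9 − 1 = 46%, not met.

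**4. Cells of the by-visit table.**
- Baseline ≤20: every class above 35 meets the criterion, but exactly 35.0 (met) is counted in >20 to ≤35.
- Baseline >20: the three classes from >20 to ≤100 are all mixed. Baseline 30 with value 40 (33% rise, not met) and with value 46 (53% rise, met) both fall in >35 to ≤50.

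**5. Do the tables together give the count?** Take four patients, all with baseline 10 ng/L, and four postbaseline samples each (a completer has Weeks 12, 24, 40 and Visit 801).

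| Patient | Set A | Set B |
|---|---|---|
| 1 | 40, 10, 10, 10 | 40, 40, 40, 40 |
| 2 | 25, 40, 10, 10 | 25, 10, 10, 10 |
| 3 | 25, 10, 40, 10 | 25, 10, 10, 10 |
| 4 | 25, 10, 10, 40 | 25, 10, 10, 10 |

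- First sample, both sets: one value of 40 and three of 25.
- Each later sample, both sets: one value of 40 and three of 10.
- Maximum table, both sets: four patients in >20 to ≤50.
- Patients reaching 35 ng/L with a rise of at least 50%: 4 in Set A, 1 in Set B.

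The values at each visit are the same in both sets, so the descriptive summaries agree as well.

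**6. What the by-visit table does give.** The number of patients ever above 35 is at least the largest single-visit count and at most the sum over visits, leaving aside values of exactly 35 and samples not assigned to a visit. Here that range is 1 to 1 + 1 + 1 + 1 = 4. Sets B and A sit at its two ends.

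**7. Unit.** 35 ng/mL = 35 × 1,000 = 35,000 ng/L, so protocol 8.1.1 and 9.2.2.4 differ 1,000-fold as written.

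**The case against.** The strongest reply is that little is lost, for five reasons.

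- **The by-visit table cuts at 35, and there are few visits.** If crossings are rare, the bounds nearly coincide. This stands, and it is why the point is about bounds and not about missing information.
- **Other any-time output exists.** SAP 6.16 plans a shift table that includes unplanned values, with Fisher's exact test, and a patient-level listing of abnormal findings. Protocol 10.3.4.4 plans any-time abnormal laboratory counts. A reader might infer that the maximum table is the only any-time summary, or that the count is unobtainable. The documents support neither. But the shift table uses low, normal and high classes, not 35 ng/L, and the listing would need counting by hand.
- **The 50% rise is a minor gap.** This stands for baselines up to about 23.3 ng/L. Above that, the rise can decide status.
- **The criterion is an individual action rule, not an endpoint.** This also stands. The endpoint is serum calcitonin, and no section promises a count of patients meeting the rule. Nor may every later value of 35 or more be read as the protocol's signal: going from 30 to 36 is a 20% rise and does not meet it, confirmation is required, and 9.2.2.4 treats patients on calcitonin-raising medication separately.
- **SAP 6.2 allows additional analyses without a SAP change.** True, but such a count would not be prespecified.

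The SAP's revision history says this part was aligned with a program SAP that is not available here. New classes might depart from its table shells, so the change is not shown to be free of cost.

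**Conclusion.** The point holds in limited form. The maximum table omits the 35 ng/L cut that the by-visit table has, and the by-visit cut differs from the protocol's at exactly 35. Together the calcitonin tables bound the per-arm number of patients reaching the threshold without giving it. The main defect is the merged >20 to ≤50 class. The absent percentage rise is secondary.

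The size in patients cannot be stated, because the documents give no calcitonin distribution. The 4-versus-1 example shows that the count is not determined; it is not an expected difference. Efficacy, power and type 1 error are untouched.

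The conclusion assumes baselines below 35 ng/L and the threshold read in ng/L. The conflict between protocol 8.1.1 and protocol 9.2.2.4 with exclusion [22] must be reconciled. This review takes no view on which unit is right.

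**What to change.** 1. Before programming, reconcile the threshold unit across protocol 8.1.1, protocol 9.2.2.4 and exclusion [22].
2. In SAP 6.13.2.4.1, use the classes ≤20, >20 to <35, ≥35 to ≤50, >50 to ≤100 and >100 ng/L in both category tables, or at least in the maximum table. This settles status for baseline ≤20 ng/L.
3. Add one row per arm: patients with any postbaseline calcitonin ≥35 ng/L and a rise of ≥50% over baseline, planned and unplanned samples included. State whether the values counted are confirmed as in protocol 9.2.2.4 or unconfirmed. Compare each dose with glargine by Fisher's exact test, the SAP 6.13 default for categorical safety data. This row covers baselines above 20 ng/L, where new classes alone are not enough.

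The row tabulates the protocol's existing rule, once reconciled, and does not alter it. The cost is a SAP wording and table-shell change with no new data. The small downside is a possible departure from the program SAP's shells, which adding the row and changing only the maximum table would limit.

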6.13.2.5. Malignancies

The AE database will be searched using predefined SMQs to identify events consistent with malignancy. Detailed searching criteria can be found in [Appendix 1](#). A summary by treatment and PT within SMQ and a listing of TEAEs will be provided. Malignancy will be considered an AESI.

6.13.2.6. Major Adverse Cardiovascular Events (MACE)

Major adverse cardiovascular events reported by investigators are adjudicated by an independent clinical endpoint committee (CEC) in a blinded fashion. The major adverse cardiovascular events (MACE) events of special interest are: deaths due to CV cause, myocardial infarction, hospitalization for unstable angina, hospitalization for heart failure, coronary interventions (such as coronary artery bypass graft [CABG] or percutaneous coronary intervention [PCI]); and cerebrovascular events, including cerebrovascular accident (stroke) and transient ischemic attack (TIA).

A listing of patients reporting MACE events, either reported by investigator or identified by the CEC, will be provided. The listing will include treatment, patient identification including the site number, date of event, type of event as reported by the investigator, type of event as adjudicated by the CEC, time from first dose of study drug to the event, and time from last dose to the event (if patient has discontinued study drug prior to the event). Only adjudication-confirmed MACE will be considered an AESI.

6.13.2.7. Arrhythmias and Cardiac Conduction Disorders

The AE database will be searched using predefined SMQs or MedDRA HLTs to identify events consistent with arrhythmias and cardiac conduction disorders. Detailed searching criteria can be found in [Appendix 1](#). Incidence of the resulting TEAEs will be summarized by treatment and PT within SMQ and HLT. Treatment-emergent severe/serious arrhythmias and cardiac conduction disorders will be considered AESIs.

6.13.2.8. Hypersensitivity Events

Hypersensitivity reactions and related information reported via the “Hypersensitivity and Anaphylactic Reactions” eCRF will be summarized by treatment. Two main analyses are performed:

- **Potential Immediate Hypersensitivity:** Analysis of TEAEs occurring from the start of study drug administration up to 24 hours after the end of study drug administration. For events without the hypersensitivity CRF, only date (no time) information is collected. Events occurring on the same date as the study drug injection date will be included.

- **Potential Non-Immediate Hypersensitivity:** Analysis of TEAEs occurring more than 24 hours after the end of study drug administration, but prior to subsequent study drug administration.

Summaries of all potential hypersensitivity reactions will be generated by PT with decreasing frequency by treatment. The AE database will be searched using predefined SMQs to identify events consistent with hypersensitivity events. Detailed searching criteria for hypersensitivity events can be found in [Appendix 1](#). Severe/serious hypersensitivity events identified by predefined SMQ searches will be considered AESIs.

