5.1. Overall Design

Study GPHO is a Phase 3, multicenter, randomized, open-label, parallel-group study that will investigate the effects of treatment with tirzepatide 5 mg, 10 mg, and 15 mg QW compared with titrated insulin glargine in patients with T2DM who have inadequate glycemic control on stable doses of metformin with or without a sulfonylurea. The primary endpoint will be the mean change in HbA1c from baseline to 40 weeks.

Patients should be on a stable dose (no dose change for at least 2 months prior to screening) of metformin alone or metformin plus a sulfonylurea. Section 2 provides a detailed schedule of activities of the study. Eligible patients will be randomized at visit 3 in a 1:1:1:1 ratio (tirzepatide 5 mg QW, tirzepatide 10 mg QW, tirzepatide 15 mg QW, and insulin glargine once daily [QD]). Patients will be stratified at randomization based on HbA1c ($\leq 8.5\%$, $> 8.5\%$ [69 mmol/mol]), country, and use of concomitant oral antidiabetic treatments (metformin alone, metformin plus sulfonylurea).

Insulin glargine will be injected QD, as a single SC injection, always at bedtime at approximately the same time every night. The initial dose of insulin glargine will be 6 IU/day for patients who have an average FBG concentration of ≥ 7.8 mmol/L (≥ 140 mg/dL). The initial dose of insulin glargine for patients with an average FBG concentration of < 7.8 mmol/L (< 140 mg/dL) may be reduced by 1-2 IU/day at the investigator's discretion. All subsequent glargine dose adjustments should be determined based on the algorithm (Kawamori et al. 2008).

[Figure GPHO.1](#) illustrates the study design.

Abbreviations: QW = once weekly; QD = once daily; SU = sulfonylurea

a Stable doses of metformin (metformin ≥ 1000 mg/day and no more than the maximum approved dose per country-specific label) and/or a sulfonylurea for 2 months prior to Visit 1, and during the Screening/Lead-in Period.

b The initial dose of insulin glargine will be 6 IU/day for patients who have an average FBG concentration of ≥ 7.8 mmol/L (140 mg/dL). The initial dose of insulin glargine for patients with an average FBG concentration of < 7.8 mmol/L (< 140 mg/dL) may be reduced by 1-2 IU/day at the investigator’s discretion.

*Telephone visits

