7.1. Treatments Administered

Patients will be randomized in a 1:1:1:1 ratio to receive tirzepatide 5 mg, 10 mg, 15 mg, or insulin glargine. Tirzepatide will be administered QW as SC injection in patients with T2DM who are already treated with a stable dose of metformin alone or metformin plus a sulfonylurea.

Table GPHO.3 shows the randomized treatments for the entire treatment period.

The starting dose of tirzepatide will be 2.5 mg QW for 4 weeks, followed by an increase to 5 mg QW, for the duration of the study for the 5-mg group. For the 10-mg group, the starting dose of tirzepatide will be 2.5 mg QW for 4 weeks, then the dose will be increased by 2.5 mg every 4 weeks (2.5 to 5 to 7.5 to 10 mg) until the 10-mg dose is reached and maintained for the duration of the study. For the 15-mg group, the starting dose of tirzepatide will be 2.5 mg QW for 4 weeks, then the dose will be increased by 2.5 mg every 4 weeks (2.5 to 5 to 7.5 to 10 to 12.5 to 15 mg) until the 15-mg dose is reached and maintained for the duration of the study.

The starting dose of insulin glargine will be 6 IU/day at bedtime, titrated to a FBG between 72-100 mg/dL, following a TTT algorithm (Kawamori et al. 2008.). During the first 8 weeks, the insulin glargine dose adjustment will be determined by the investigator in discussion with the patient. From week 8 onwards, the decision of the titration will be made and implemented by the patient in a weekly manner. Between Week 8 and Week 16, investigators or study site personnel will contact the patient every 2 weeks (office or telephone visit) and will review the insulin dose adjustment made by the patient at each of these visits.

Table GPHO.3. Treatment Regimens

Name of Study Drug	Dosage	Frequency	Drug Formulation	Route of Administration
Tirzepatide	5 mg ^a	QW	Single-dose pen	SC
	10 mg ^a	QW	Single-dose pen	SC
	15 mg ^a	QW	Single-dose pen	SC
Insulin glargine	TTT dosing ^b	QD	prefilled pen	SC

Abbreviations: QD = once daily; QW = once weekly; SC = subcutaneous; TTT = treat-to-target.

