6.10.2. Exposure and Compliance to Insulin Glargine Treat-to-Target Algorithm

Summary information on total daily dose of insulin glargine will be reported by visit. Information related to compliance to treat-to-target therapy including reasons for non-compliance will be summarized.

Compliance will be defined as taking at least 75% of the scheduled insulin doses. The number of insulin doses administered was calculated by subtracting the number of doses missed as entered in the compliance CRF from the number of doses expected to be administered. Compliance will be calculated by taking the number of doses administered (regardless of the actual dose administered) divided by the total number of doses expected to be administered $\times 100$. Treatment compliance will be summarized descriptively over the entire study period by treatment using the mITT population

Additionally, summaries will be produced for the percent of patients to reach fasting serum glucose goals of <100 mg/dL (5.6 mmol/L) and <126 mg/dL (7 mmol/L) over time at weeks 16, 24, and 40.

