6.13. Safety Analysis

Unless specified otherwise, safety assessments will be based on the SS ([Table GPHO.6.1](#)). All events that occur between the date of first dose of study drug to the date of patient's safety follow-up visit or patient's end of study participation will be included, regardless of the adherence to study drug or initiation of rescue therapy. The events occurring on the day of the first dose of study medication will be counted as post-treatment. For assessing benefit and risk profile through 40-weeks, selected safety analyses will be conducted by utilizing safety data from first dose through the date of 40-week visit. Some safety analyses may be conducted after excluding data after the initiation of new antihyperglycemic therapy. Unless specified otherwise, statistical assessment of homogeneity of the distribution of categorical safety responses among treatment arms will be conducted using Fisher's exact test.

The mean change from baseline difference among treatment at all scheduled visits will be assessed via a MMRM using REML. The model will include country, baseline HbA1c ($\leq 8.5\%$, $> 8.5\%$ [≤ 69 , > 69 mmol/mol]), baseline concomitant oral antihyperglycemic medication, treatment group, visit, and treatment-by-visit interaction as fixed effects, and baseline value of the safety parameter as a covariate. To model the covariance structure within patients, the unstructured covariance matrix will be used. If this model fails to converge, the covariance structures will be tested in order specified in Section 6.12.1.1.

For selected safety parameters, time-to-first-event analysis via the cox-proportional hazards model may be conducted. Patients without the event will be censored at the end of study participation. For patients experiencing the event, the “time-to-first-event” will be the time (in days) from first dose to first occurrence of the event.

Where necessary, the rate of events will be analyzed using a generalized linear mixed-effects model assuming the number of events follow a negative binomial distribution, and with treatment as a fixed effect. The logarithm of days during the active treatment period will be adjusted as an offset to account for possible unequal treatment duration of follow-up between patients.

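### The immediate and non-immediate hypersensitivity rows cannot be compared between daily glargine and weekly tirzepatide, because dosing frequency sets how much time each row covers

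*SAP*

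**What the plan says.** SAP 6.13.2.8 (Hypersensitivity Events) summarizes hypersensitivity by treatment and states: "Two main analyses are performed". Both are defined only by time since the last dose. The immediate analysis runs from the start of administration to 24 hours after its end. The non-immediate one is "Analysis of TEAEs occurring more than 24 hours after the end of study drug administration, but prior to subsequent study drug administration". Where an event has a date but no clock time, the immediate row uses this rule: "Events occurring on the same date as the study drug injection date will be included".

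The same section also plans a summary that is not split by time: "Summaries of all potential hypersensitivity reactions will be generated by PT with decreasing frequency by treatment". AESIs are the severe or serious events found by SMQ search, again whatever their timing.

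The dosing intervals come from the protocol. Section 5.1 says "Insulin glargine will be injected QD, as a single SC injection, always at bedtime at approximately the same time every night", and section 7.1 says "Tirzepatide will be administered QW as SC injection in patients with T2DM".

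SAP 4.4 lists the incidence of allergic and hypersensitivity reactions among the outcomes on which tirzepatide is compared with glargine. SAP 6.2 limits treatment comparisons to tirzepatide doses against glargine. SAP 6.13 sets Fisher's exact test as the default: "statistical assessment of homogeneity of the distribution of categorical safety responses among treatment arms will be conducted using" that test. Section 6.13.2.8 names no test of its own. It does not restrict the timed rows to tirzepatide, adjust for time at risk, or warn against comparing them across arms.

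**The concern.** A 24-hour window after each dose spans nearly all on-drug time for a once-daily drug and about one seventh of it for a once-weekly drug. The non-immediate window is the remainder: near-empty for glargine, about six sevenths for tirzepatide. A rash unrelated to either drug is therefore filed as immediate on glargine and usually as non-immediate on tirzepatide.

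The two rows mislead in opposite directions. The immediate row favours tirzepatide and can hide or reverse a real excess of reactions soon after injection. The non-immediate row can suggest a tirzepatide problem where none exists. Neither answers the stated safety objective, which is overall incidence, yet the section gives these rows main status.

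**Working it through.** The plan gives no figure on this point, so there is none to reproduce.

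**Inputs from the documents.** Treatment lasts 40 weeks = 280 days (Protocol 5.1), which means 280 daily or 40 weekly doses. There are 239 patients per arm (Protocol 5.2). The compliance floor is 75% of doses (SAP 6.10.1 for tirzepatide; 6.10.2 for glargine, "Compliance will be defined as taking at least 75% of the scheduled insulin doses").

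**Assumptions.** The background incidence p over 40 weeks is equal in all arms and evenly spread over time. The documents give no rate, so p = 1%, 2%, 3%, 5% and 8% are used.

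**Time in each row, all doses taken**
- Immediate: glargine 280/280 days; tirzepatide 40/280; ratio 280/40 = 7.
- Non-immediate: glargine 0/280; tirzepatide 240/280 = 85.7%.
- The date-only rule gives the same shares: 7 of 7 dates against 1 of 7.

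The 7:1 is glargine against one tirzepatide arm. Against the three arms pooled, raw counts would be 7:3, and the per-patient ratio would still be 7:1.

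**Row incidences.** Let a be the share of doses taken, equal in both arms.
- Immediate: a·p (glargine) against a·p/7 (tirzepatide).
- Non-immediate: (1 − a)·p against (1 − a/7)·p.

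For example, at p = 5% and a = 1, the immediate row expects 239 × 0.05 = 12.0 against 239 × 0.05/7 = 1.7 patients.

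**Exact probability of two-sided Fisher p < 0.05 with no true difference, one dose against glargine**

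| p | Immediate, expected patients (glargine vs tirzepatide), a = 1 | Immediate flagged, a = 1 | Non-immediate flagged, a = 1 | Immediate flagged, a = 0.75 | Non-immediate flagged, a = 0.75 | Unsplit flagged |
|---|---|---|---|---|---|---|
| 1% | 2.4 vs 0.3 | 2.5% | 1.8% | 0.8% | 1.2% | 0.8% |
| 2% | 4.8 vs 0.7 | 21% | 23% | 10% | 10% | 2.0% |
| 3% | 7.2 vs 1.0 | 46% | 58% | 28% | 23% | 2.5% |
| 5% | 12.0 vs 1.7 | 78% | 94.5% | 60% | 46% | 3.1% |
| 8% | 19.1 vs 2.7 | 96% | 99.9% | 87% | 73% | 3.5% |

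A constant-hazard model, with tirzepatide immediate incidence 1 − (1 − p)^(1/7), gives nearly the same: at 5%, a ratio of 6.85 and flag rates of 77% and 95%.

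**Sensitivity of the window shares**
- Equal missed doses leave the immediate ratio at 7:1. The non-immediate ratio, (1 − a/7)/(1 − a), is 17:1, 8.7:1 and 3.6:1 (tirzepatide to glargine) at 95%, 90% and 75% of doses.
- Bedtime variation with an SD of 1 hour gives 6.8:1 in the immediate row and 37:1 in the non-immediate row.
- Counting 28 days after the last dose as non-immediate, the immediate window covers 280/308 = 91% against 40/308 = 13% of days. The non-immediate ratio is 268/28 = 9.6. The SAP does not say where this time belongs, since no dose follows it.

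**Reversal.** Let d be a true excess of immediate reactions on tirzepatide, with a = 1. The immediate row shows p/7 + d on tirzepatide and p on glargine, so the direction reverses when d < 6p/7. With d = 2%:
- p = 5%: 2.7% against 5.0%, reversed (6p/7 = 4.3%). Unsplit: 7.0% against 5.0%.
- p = 2%: 2.3% against 2.0%, right direction but much diluted (6p/7 = 1.7%). Unsplit: 4.0% against 2.0%.
- p = 1%: 2.1% against 1.0%, right direction. Unsplit: 3.0% against 1.0%.

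**The case against.** The strongest reply is that a fair comparison is already in the plan. The unsplit summary and the SMQ-based AESI rule ignore time since dose. SAP 6.13.1 applies between-arm comparisons to all TEAEs by preferred term and system organ class. The Fisher default that reaches the timed rows reaches the unsplit ones too, and no type 1 error-controlled decision uses any of them. This stands, and it confines the damage to the two timed rows. It does not supply what the section lacks: a named patient-level comparison of any hypersensitivity TEAE.

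Second, the even-spread model fits only some events. Protocol 9.2.2.7 collects the additional CRF data for events the investigator judges drug-related, and those may cluster after doses. This also stands, so the 7:1 applies to background events only. But 6.13.2.8 expressly admits events without that CRF and runs SMQ searches, and the documents do not show how much of each row is background.

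Third, the high false-flag rates depend on assumed rates. At 1% background, both timed rows are flagged less often than the nominal 5%. That is correct, but the skew in expected counts is the same at every rate, and percentages printed side by side can mislead without a test.

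Fourth, the timing split has a clinical purpose: Protocol 9.4.4 itself distinguishes immediate from non-immediate reactions. It does, within a drug of one dosing interval. That is a reason to keep the split for tirzepatide, not to set it against a daily injection.

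**Conclusion.** The concern holds. As written, the two main hypersensitivity rows are largely determined by dosing frequency for background events. The immediate row is about 7:1 towards glargine, whatever the equal level of adherence. The non-immediate row is almost only tirzepatide near full adherence, falling to about 3.6:1 if only 75% of doses are taken. These ratios assume an equal, evenly spread background rate. How often a test would flag them depends on that rate, which the documents do not give. A true excess of immediate reactions on tirzepatide is reversed in the immediate row only when it is below six sevenths of the background rate. Overall incidence remains assessable from the unsplit data, so the safety objective is not lost. The section's main rows do not serve it, however, and should be changed.

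**What to change.** In SAP 6.13.2.8, define the between-arm analysis as the number and percentage of patients with any potential hypersensitivity TEAE, both windows combined, each tirzepatide dose against glargine. Keep the immediate/non-immediate split as a descriptive table within the tirzepatide arms, with no test against glargine. A footnote saying that the timed rows are not comparable across dosing intervals would be a weaker remedy, because it leaves those rows as the main analyses.

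The cost is SAP wording only, with no new data. What is lost is a split contrast with glargine that dosing frequency largely determines.
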